7.7.2. Immunogenicity Statistical Methodology

All analyses will be done for all four ADA assessments (ADA, NAb, M2 reactivity and GLP-2 cross-reactivity), unless otherwise specified.

The overall anti-glepaglutide antibody incidence (sum of treatment boosted and treatment induced) will be tabulated by treatment group and visit, and overall (incidence of patients ADA positive any time during trial). Similar tables will be made separately for treatment boosted and treatment induced ADAs, if both types are observed. In addition, the ADA incidences by visit will be presented graphically.

For all treatment induced ADA positive patients, the titer levels will be summarized by treatment group and visit using descriptive statistics including median, geometric mean, geometric CV%, inter-quartile range, minimum, maximum, and number of observations (positive samples only).

For all treatment boosted ADA positive patients (if applicable), the titer levels and fold increases from baseline of titers will be summarized by treatment group and visit using descriptive statistics including median, geometric mean, geometric CV%, inter-quartile range, minimum, maximum, and number of observations (positive samples only).

Spaghetti plots of individual trajectories over time of ADA titers (and fold increases of ADA titers, if applicable) will be presented for each treatment group. Plots of the geometric mean ADA titers by visit and treatment group will be presented.

All immunogenicity data will be listed, including corresponding PK concentrations.

Investigating immunogenicity impact on efficacy and safety

To assess the impact of ADA on efficacy and safety, the results for each of the ADA assessments (ADA, NAb, M2 reactivity and GLP-2 cross-reactivity) will be categorized into three levels (negative, low titer positive, and high titer positive).

The ADA results will be grouped as either 1) or 2):

25 August 2022

- (1) ADA status/titer, if more than 5 patients have positive outcome in the assessment:
 - a. Level 1: ADA negative
 - b. Level 2: ADA low titer positive (titers \leq median titer at Week 24)
 - c. Level 3: ADA high titer positive (titers > median titer at Week 24)
- (2) ADA status/titer, if 5 patients or less have positive outcome in the assessment:
 - d. Level 1: ADA negative
 - e. Level 2: ADA positive

The median titer at Week 24 will be calculated for the ADA positive samples only.

Immunogenicity association with PK

The analysis of ADA association with PK will be made for all analytes, i.e. for the conceptual concentration (glepaglutide), the parent compound (parent) and the two main metabolites (M1 and M2) and using the assessments ADA and M2-reactivity only.

In cases, where an analyte will only contribute to a particular analysis with concentrations <LLOQ, the analysis will be omitted for that analyte.

The potential association between ADA and PK will be investigated graphically, by plots of individual observed trough concentrations by treatment and visit (Day 1, W2, W4, W8, W12, W24), where observations with ADA measurements at the same visits are marked according to the observed ADA titer categories defined above. A concentration is considered a trough measurement if taken more than 60 hours after the preceding dose of glepaglutide. The plots will also be made where all observations for each subject are marked according to the ADA level of the patient at week 24.

Similar plots will be made for all observed concentrations, regardless of timing of assessment relative to last dose.

Immunogenicity association with efficacy

The analysis of ADA association with efficacy will be made for the primary endpoint, change from baseline in actual PS volume, and using all four ADA assessments (ADA, NAb, M2-reactivity, and GLP-2 cross-reactivity).

The potential association between ADA and efficacy will be investigated graphically, by plots of individual trajectories of change from baseline in actual PS volume (L/week) by treatment and visit (Day 1, W2, W4, W8, W12, W24), where observations with ADA measurements at the same visits are marked according to the observed ADA titer category defined above. The plots

will also be made where observations for each subject are marked according to the ADA titer category of the patient at week 24.

Plots by treatment of individual change from baseline in actual PS volume (L/week) at week 24 versus titer values at week 24, will also be presented.

Immunogenicity association safety

The potential association between ADA and safety will be investigated by summarizing selected types of treatment emergent adverse events (TEAEs) by severity and seriousness by ADA titer category at Week 24 as defined above.

AEs which could potentially be associated with ADA include injection site reactions and conditions which may reflect immune-mediated adverse events, such as hypersensitivity reactions, infusion reactions, and inflammatory responses secondary to immune complex or complement-mediated reactions.

In addition, the potential association between levels of ADA, neutralizing ADA, or ADA binding to M2, or cross-reacting with human GLP-2 (endogenous counterpart), and AEs related to lack of efficacy will be investigated.

The AEs of interest will be selected according to the following definitions and MedDRA SMQs:

- Lack of efficacy/decreased drug effect (using the assessments ADA, NAb activity, M2 reactivity, and GLP-2 cross-reactivity) (Extracted with the MedDRA SMQ: Lack of efficacy/effect (narrow scope))
- (2) Injection site reactions (using the assessment ADA only) (captured using the CRF tick mark 'study treatment injections site reaction')
- (3) Allergic reactions (using the assessment ADA only) (Extracted with the following MedDRA SMQ: Hypersensitivity (broad scope)

Further analyses of associations between ADA and PK, efficacy or safety will be made if suggested by the graphical evaluations and summary statistics.

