5. GENERAL ASPECTS FOR STATISTICAL ANALYSIS

5.1. GENERAL METHODS

- All analyses and summaries will be produced using SAS version 9.4 (or higher).
- Continuous variables will be summarized using the number of patients with evaluable data, mean (or geometric mean), standard deviation (or coefficient of variation), median, minimum and maximum. The same number of decimal places as in the raw data will be presented when reporting minimum and maximum, 1 more decimal place than in the raw data will be presented when reporting the mean and median, and 2 more decimal places than in the raw data will be presented when reporting the SD.
- Categorical variables will be summarized using the number of observations (n), frequency and percentage of patients. All percentages will be presented as one-decimal point, unless otherwise specified. Percentages equal to 100 will be presented as 100% and percentages will not be presented for zero frequencies.
- Unless stated otherwise, the percentages will be based on the number of non-missing observations. Treatment group headers will still contain the number of patients in the treatment group. If applicable, a row for the number of non-missing observations in the table (at each time point) for each variable will be included as part of the descriptive statistics.
- All comparisons will be between each ZP1848-17111 treatment group and placebo.
- Any calculated p-values will be presented to 3 decimal places; p-values less than 0.001 will be presented as 'p<0.001' and p-values greater than 0.999 will be presented as 'p>0.999'.
- All relevant patient data will be included in listings and sorted by treatment group, patient ID, and visit, as applicable, for all patients relevant for the listing.
- Unscheduled or repeat assessments will not be included in summary tables unless specified otherwise, but they will be included in the patient listings.
- All tables, listings and figures will include footers that identify the name of the program that created the item, together with the date and time on which it was created. Headers will include the total number of pages that the presentation contains and, for each page, the number of the page within the presentation.

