5.3. MISSING DATA AND DATA HANDLING RULES

Every effort will be made to collect all data at specified time points, according to the schedule of trial events. Reasons for withdrawal from the trial will be recorded on the eCRF.

For actual weekly PS volume, a detailed algorithm is included in Appendix A. In brief, for each visit, the actual weekly PS volume will be derived by using a valid 7-day period closest to the visit where

1. the actual weekly PS volume accounted for \geq 90% of prescribed weekly PS volume

or

2. there is at least one actual PS volume accounted for by the patient in the eDiary for each day in the valid 7-day period

For all post-baseline visits, the 7-day period is allowed to start up to 14 days before a visit, provided that it does not start before the previous visit. For baseline visits, the 7-day period is allowed to start up to 30 days before the baseline visit, provided that it does not start before the latest optimization visit. The Day 3 and Week 1 visits are not included in the calculations.

Note that, if the last PS prescription during the treatment period has been stopped more than 7 days prior to a visit, and there are no entries of actual PS volumes recorded by the patient in the eDiary within 7-days prior to this visit then the actual weekly PS volume will be set to zero.

The efficacy endpoints will be missing at visits, where no valid 7-days period can be found based on the above algorithm.

Any missing data during the trial prior to trial completion or discontinuation will remain as missing at that time point. However, several multiple imputation methods will be used to impute missing data for the primary efficacy endpoint as well as for the key secondary efficacy endpoints. See 5.3.1 for details of the multiple imputation method.

Imputation rules for the handling of missing data for PROs and health economic assessments will follow rules per each assessment manual.

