7.7. IMMUNOGENICITY

7.7.1. Immunogenicity Assessment

A serum sample is defined as anti-drug antibody (ADA)-positive if results of the antiglepaglutide antibody screening and confirmatory assays are positive. If positive, a titer (highest dilution factor that still yields a positive reading) will be reported. Patients without any ADA data (evaluable samples) will be excluded from the analysis.

- 1. Pre-existing ADA (Yes/No) is defined, at the patient level, by the ADA status at trial baseline (i.e. Day 1), according to the presence or absence of ADA. This endpoint is defined for any patient with a valid ADA assessment at Day 1.
- 2. A treatment-boosted ADA positive patient (Yes/No) is defined, at the patient level, as any occurrence during the trial of at least a 4 fold increase from trial baseline in ADA-titer for patients with pre-existing ADA (and a titer at baseline).
- 3. A treatment-induced ADA positive patient (Yes/No) is defined, at the patient level, as any occurrence of ADA during the trial for patients without pre-existing ADA (based on a negative baseline ADA measurement).
- 4. An ADA positive patient (Yes/No) is defined by being either a treatment-boosted or treatment-induced ADA positive during the trial (for patients with a baseline ADA measurement).

Confirmed positive ADA samples will be further evaluated in three different ADA characterization assays: for in *vitro* glepaglutide neutralizing potential (NAb), for reactivity to the predominant metabolite (M2) and for cross-reactivity towards GLP-2. In case of a positive result in the ADA characterization assays, a titer will be estimated.

Confidential

For ADA negative samples, the missing assessments for in vitro glepaglutide neutralizing potential (NAb), for reactivity to the predominant metabolite (M2) and for cross-reactivity towards GLP-2 will be considered negative in all below analyses and presentations.

In case of positive results at study baseline (Day 1) in the ADA characterization assays ('Preexisting NAb', 'pre-existing M2 reactivity', 'pre-existing GLP-2 cross-reactivity'), the definitions and calculations for pre-existing ADA and treatment boosted ADA will correspondingly apply.

In case of a negative assessment in either of the four assays (ADA, NAb, M2 reactivity and GLP-2 cross-reactivity) the titer value will be set to ¹/₄ MRD (Minimal Required Dilution) for illustration purposes.

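### The only planned ADA-safety summary groups adverse events by ADA category at Week 24, so patients with a transient ADA response are shown as ADA negative; the safety analysis is incomplete without a summary by the SAP's own any-time ADA status.

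*SAP*

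**What the plan says.** **The safety summary.** In SAP 7.7.2, the part on ADA and safety plans "summarizing selected types of treatment emergent adverse events (TEAEs) by severity and seriousness by ADA titer category at Week 24 as defined above". The selected events are lack of effect, injection site reactions and allergic reactions. The categories are set out earlier in the same section: negative, low-titer positive and high-titer positive, split at the median Week 24 titer of the positive samples. They reduce to negative and positive when five or fewer patients are positive. SAP 7.2 counts an event as treatment-emergent from the first day of exposure.

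**The patient-level definition.** Under SAP 7.7.1, an ADA positive patient "is defined by being either a treatment-boosted or treatment-induced ADA positive during the trial". Treatment-induced means that ADA is found at any time in a patient who was negative at baseline. It need not last to Week 24. The incidence tables in 7.7.2 include an overall figure, described as the "incidence of patients ADA positive any time during trial".

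**PK and efficacy.** Both sets of plots in 7.7.2 are marked twice: by the ADA category seen at the same visit, and by the patient's category at Week 24.

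**Other displays.** SAP 7.7.2 also plans "Spaghetti plots of individual trajectories over time of ADA titers" and a listing of all immunogenicity data. It closes with: "Further analyses of associations between ADA and PK, efficacy or safety will be made if suggested by the graphical evaluations and summary statistics".

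**Missing results.** SAP 7.7.1 says "Patients without any ADA data (evaluable samples) will be excluded from the analysis". SAP 5.1 adds that, unless stated otherwise, "the percentages will be based on the number of non-missing observations". SAP 5.3 says "Any missing data during the trial prior to trial completion or discontinuation will remain as missing at that time point".

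**Protocol.** Section 11.3.6.6 schedules ADA samples at Day 1, Weeks 2, 4, 8, 12 and 24, and at follow-up where it applies. Section 4.3.2 rates the risk of an ADA response as high, leaves open whether it is transient or lasting, and rates its consequences so far as minor.

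**The concern.** The events run from the first dose, but the grouping variable is a single reading at the end of treatment. An injection site reaction at Week 4 in a patient who was antibody positive at Week 4 and negative at Week 24 would be counted in the ADA negative row. The SAP's own patient-level definition calls that patient ADA positive, and no planned table crosses that definition with adverse events.

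The protocol treats transience as an open question, and the selected events are not limited to late onset. A reader of the clinical trial report who wants to know whether patients who ever made antibodies had more of these events would find no table that answers it. What is at stake is the completeness of a descriptive safety display, not a test result.

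**Working it through.** The plan states no figure on this point, so none can be reproduced. The check traces patients through the two classifications. It takes the category at Week 24 to mean the result of the Week 24 sample.

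| Patient | Status under SAP 7.7.1 | Any-time incidence, SAP 7.7.2 | Row in the ADA-safety summary, SAP 7.7.2 |
|---|---|---|---|
| Negative at Day 1 and at every later sample | Not ADA positive | Not counted | Negative |
| Negative at Day 1, positive at Week 24 | Treatment-induced, so ADA positive | Counted | Low or high titer (or positive) |
| Negative at Day 1, positive at one or more of Weeks 2, 4, 8 and 12, negative at Week 24 | Treatment-induced, so ADA positive | Counted | **Negative** |
| Negative at Day 1, positive at one or more of Weeks 2, 4, 8 and 12, no Week 24 sample | Treatment-induced, so ADA positive | Counted | **None assigned** |

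**Third row.** The two classifications differ. Events that occurred while this patient was antibody positive are summarized as events in an ADA negative patient.

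**Fourth row.** The patient has ADA data and so is not excluded by 7.7.1. The general rules leave the Week 24 result missing and outside the percentages. One thing remains unsettled. SAP section 11, footnote 11, asks patients who stop treatment for an ADA sample at end of treatment. SAP 3.1 labels an early end-of-treatment visit Visit 10, the same number as the Week 24 visit, but its re-allocation rule is written for PS volume. Nothing says whether an early end-of-treatment ADA sample counts as Week 24.

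**Direction of the effect.** Let n_P, n_T and n_N be the numbers of patients positive at Week 24, transiently positive, and never positive. Let r_P, r_T and r_N be the proportions with a given event. For simplicity, leave out patients with missing results or with pre-existing ADA.

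- Week 24 grouping: difference = r_P − (n_T·r_T + n_N·r_N)/(n_T + n_N)
- Any-time grouping: difference = (n_P·r_P + n_T·r_T)/(n_P + n_T) − r_N

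Three limiting cases:

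- If r_T = r_P, the Week 24 difference is (r_P − r_N)·n_N/(n_T + n_N), which is diluted. The any-time difference is r_P − r_N.
- If r_T = r_N, the Week 24 difference is r_P − r_N. The any-time difference is (r_P − r_N)·n_P/(n_P + n_T), which is diluted.
- If n_T = 0, both equal r_P − r_N.

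The documents give none of these six quantities, so neither the size nor the direction can be fixed in advance.

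**The case against.** **The two definitions serve different purposes.** SAP 7.7.1 defines incidence at patient level, while 7.7.2 sets titer levels for judging impact. A row for patients negative at Week 24, in a table labelled as Week 24, is correctly labelled. This stands. A reader might infer that the SAP contradicts itself or mislabels patients, and the documents do not support that. They show that one useful grouping is absent.

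**The phrase about categories defined above might mean any-time status**, with Week 24 fixing only the median cut-off. This is a weak reading. The sentence places the category at Week 24, the parallel efficacy sentence speaks of the patient's category at that week, and the negative level is not tied to the definition in 7.7.1.

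**Transient responses are not hidden.** The titer trajectories, the ADA listing and the listing of all treatment-emergent events allow linkage by patient. Protocol 11.4.3 asks for an ADA sample 2 to 4 weeks after a potential hypersensitivity reaction. Protocol 6.1 asks for samples at end of treatment and about four weeks after discontinuation. These help with individual cases and they stand as mitigation. None of them is a summary by group, and the clause on further analyses is conditional and names no method.

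**Any-time status has faults of its own.** The first positive sample may follow the event, and patients who stop early have fewer scheduled chances to test positive. This stands, and it is why the added table should not replace the planned one.

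**The missing-sample point is mostly one of display.** That is fair, except for the unsettled status of the early end-of-treatment sample.

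**Conclusion.** The point holds as a minor gap. PK and efficacy are each shown by same-visit and by Week 24 category. Safety is shown by Week 24 category alone, with no any-time or visit-matched grouping. The trace above rests on the plain reading of the Week 24 category and is firm. The consequence is not quantifiable: it is nil if no positive patient reverts by Week 24, and otherwise depends on how many do and on their event risk.

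A reader might infer that the planned table must hide or weaken an ADA-safety association. That would require transient responders to have an event risk closer to that of persistent responders than to that of never-positive patients. The documents do not say so, and Protocol 4.3.2 reports no adverse events linked to the immune response so far. Nor is any confirmatory conclusion affected: the summary is descriptive, and SAP 3.6 plans no inferential tests of safety data.

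**What to change.** In SAP 7.7.2:

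1. Keep the summary by Week 24 category.
2. Add one descriptive summary of the same events by the patient-level status exactly as 7.7.1 defines it: treatment-induced or treatment-boosted during the trial, versus not. Show separately patients with pre-existing ADA that was not boosted, who carry antibody but are not ADA positive by that definition, and patients with no baseline ADA result, to whom the definition does not apply.
3. In the Week 24 summary, give patients without a Week 24 sample their own row.
4. State whether an early end-of-treatment ADA sample counts as Week 24.
5. Footnote the any-time summary: the first positive sample may come after the event, and patients who stop early have fewer scheduled samples.

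The cost is a few sentences of SAP text and a little extra descriptive output from data already collected. No extra sampling is needed, and the confirmatory analyses are unchanged.

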8. CHANGES FROM PROTOCOL

Protocol Section	SAP Section	Summary of Change
12	3	• For the primary, the key secondary efficacy endpoints and the endpoints related to the macro- and micro-nutrients (all derived from actual PS), sensitivity analyses will be made based on a valid 14-days period prior the relevant visits.
12.3	3.0	• Efficacy endpoint descriptions have been updated using the word "change" instead of "reduction".
N/A	3.1	• Added a COVID-19 statement that no sensitivity analyses will be done to assess the impact of COVID-19, and cited reference document describing COVID-19 continency plans for glepaglutide phase 3 trials. This text does not appear in the protocol.
12.3.4	3.4	• For the secondary efficacy endpoint of Change in weight from baseline to Week 24 , the BMI subgroup categories were updated to match the BMI subgroup categories used in the ISS. In addition, a shift table from baseline to Week 24 by BMI subgroup categories has been added.
12.3.4	3.5	• Graphical presentations of urine volume, fluid intake together with PS vol, have been added. The presentations replace the MMRM analyses of FCE described in the protocol.
12.4	3.7	• The nomenclature of the conceptual analyte glepaglutide (parent + M1 + M2) was changed compared to the protocol.
12.2	4.0	• The Per-protocol Analysis Set has been deleted as a trial analysis set and replaced with a supplementary estimand using a hypothetical strategy assuming missing data to be missing at random (MAR).
12.6	5.3	• The algorithm defining when and how weekly PS volume is calculated and when it is considered missing is included.
12.7	5.3.1	• For the multiple imputation method, the number of imputed datasets changed from 1000 to 100.

9. CHANGES FROM PREVIOUS SAPS

SAP version	SAP section	Summary of change	Rationale for change
$5.0 \rightarrow 6.0$	General	• Editorial changes throughout e.g. document version, dates, table and figure references, addition/removal of sections, changes to header titles etc.	• To have a coherent document
$5.0 \rightarrow 6.0$	1.1	Responsibility of TFL generation transferred to Zealand Pharma	• To reflect internal strategic decision
$5.0 \rightarrow 6.0$	2.3	Editorial changes	• To make the specification of primary estimand of primary endpoint clear
		• Addition of supplementary estimand	• To make the specification of supplementary estimand of primary endpoint clear
$5.0 \rightarrow 6.0$	3.1	• Introduction of terminology main estimator and sensitivity estimators	• For ease of reference
		 Addition two sensitivity analyses Tipping point analysis Analysis on all observed data 	• To further explore robustness of primary analysis of primary endpoint in terms of missing data assumptions under which the conclusions change and impact of using multiple imputation methods, respectively
		• Addition of Table 3	• To provide a better overview of the various estimands and estimators, and how missing data is handled
		• Addition of Week 1 to the primary analysis model	• To accurately determine the study drug's treatment effect in the early weeks
$5.0 \rightarrow 6.0$	3.1.1	• New section divider added	• For ease of navigation
		• Definition of collapsing PGIC groups redefined	• Collapsing of groups is now made based on current data distribution to

SAP version	SAP section	Summary of change	Rationale for change
		• Spearman rank-order and Kendall's tau-b correlation coefficients added	 support interpretation in the best possible way To further specify the type of correlation coefficients used. The coefficients are chosen based on their typical use in psychometric evaluation of assessment tools
$5.0 \rightarrow 6.0$	3.1.2	New section divider added	For ease of navigation
$5.0 \rightarrow 6.0$	3.1.3	New section divider added	• For ease of navigation
$5.0 \rightarrow 6.0$	3.1.4	• New section introduced with addition of supportive analyses for primary endpoint derivation (actual weekly PS volume)	• To explore robustness of the primary statistical analysis with regard to the primary endpoint derivation
$5.0 \rightarrow 6.0$	3.2	• Primary and supplementary estimand has been defined for each key secondary efficacy endpoint	• To further clarify the clinical question of interest and have a precise description of the treatment difference estimated for each of the key secondary efficacy endpoints
		• Primary and sensitivity analysis for primary estimand, and primary analysis for supplementary estimand are now defined for each key secondary efficacy endpoint	• To avoid any misalignment with assessment of robustness of primary estimate for each of the key secondary efficacy endpoints
		• Addition of Table 6	• To provide a better overview of the various estimands and estimators, and how missing data is handled
25 August 20		• For binary key secondary efficacy endpoints, the method for weighing and estimating CIs and type of test have been specified, along with a model Confidential	• The exact model specifications are needed before unblinding as these are confirmatory endpoints Page 52 of 65

SAP version	SAP section	Summary of change	Rationale for change
		simplication procedure in case of zero strata occurrence	
		• For binary key secondary efficacy endpoints, Wilson- Hilferty transformation has been specified for the sensitivity analysis (using CR-imputed values)	• To handle asymptotics of Cochran- Mantel-Haenszel test under the null hypothesis of no association and applying Rubin's rule
$5.0 \rightarrow 6.0$	3.3	• New high-resolution figure added	• Text in figure was not readable before
$5.0 \rightarrow 6.0$	3.4	• Addition of endpoint 'Reduction of at least 30% in actual weekly PS volume from baseline to both Weeks 20 and 24'	• To further explore different definitions for clinical response based on the outcome of the clinical meaningfulness analysis specified in 3.1.1
		• Addition of endpoint 'Reduction in prescribed weekly PS volume of 100% (weaned off) at Week 24'	• The endpoint is considered clinically relevant and thus should be prespecified
$5.0 \rightarrow 6.0$	5.3	Algorithm updated	• To align with Appendix A
5.0 → 6.0	5.3.1	Removal of tuning and thinning specifications for non-monotone MCMC procedures	• The impact of specifying these technical details in terms of convergence of the MCMC method is considered negligible, and hence not considered for the programming. Imputations of non-monotone missing data pattern will be performed using the MCMC statement in PROC MI
		• Addition of Week 1 to imputation model	• To accommodate inclusion of Week 1 in the primary statistical model
$5.0 \rightarrow 6.0$	5.3.2	Biserial correlation coefficient replaced with Spearman rank-order and	• To align with section 3.1.1. The biserial correlation coefficient is

SAP version	SAP section	Summary of change	Rationale for change
		Kendall's tau-b correlation coefficients	used when there is one dichotomous variable, which is not the case
$5.0 \rightarrow 6.0$	7.2	• Definition of AEs leading to withdrawal added	• As AEs leading to trial withdrawal are not readily available in data as collected, a need to define a conservative rule to identify these events was deemed necessary
		• Definition of common AEs added	• For ease of reference at time of reporting
$5.0 \rightarrow 6.0$	13	• Section 'Table of Contents for Tables, Listings, and Figures' deleted	• This is not considered mandatory for a SAP and is specified elsewhere
$5.0 \rightarrow 6.0$	А	• New terminology introduced (e.g. accounted for) and further clarification text added, and minor typos corrected	• To ensure the algorithm reads well
		• Allowing to look further back in time for a valid period for baseline specifically	• To allow a window of identifying a valid period for baseline aligned with the CTP (stabilization period between 2-4 weeks), i.e. using data from a period considered clinically representable of baseline
		• Not allowing to use data points from the optimization period	• In this period the patients are not considered stable
		• An exemption to the step 2 rule of a valid period cannot start before the previous visit for post-baseline visits , has been implemented for Week 1 (in addition to Week 2)	• To accommodate inclusion of Week 1 in the primary statistical model
$5.0 \rightarrow 6.0$	В	• Two additional references added	• References necessary after updates to the SAP

